## 1. Summary

### Background

Ultrasound examinations have become an integral part of everyday clinical practice. Ultrasound imaging impresses with a combination of availability, freedom from radiation and high diagnostic gain. So far, however, it is above all the diagnostic gain that must be critically questioned, as ultrasound examinations are strongly dependent on the examiner. Especially for the evaluation of ultrasound images, a wealth of experience is necessary. A more objective evaluation is offered by the technique of quantitative ultrasound (QUS). A quantitative evaluation of so-called RF data (radiofrequency data) enables a more accurate diagnosis that is independent of the assessor. The gain in information is similar to the change from black-and-white television to color television. Physically, this is based on the individual, frequency-dependent sound reflection of tissues and pathologies depending on their biomechanical properties. This makes it possible, for example, to automate the segmentation of ultrasound images or the early detection of hepatic steatosis. Previous systems are based on narrowband piezo transducers, which is why a broadband analysis of tissue properties in the clinical setting has not yet been carried out. The approach is thus like promising ex-vivo studies, such as Gare et al., 2022, Nguyen et al., 2021 and Gangeh et al., 2014.

### Goal

Within the framework of basic research, multicenter *prospective*, anonymized, broadband raw ultrasound data are to be collected for the first time in a common database. The basis for this database is the cooperation of several German centers (previously planned: University Hospital Dresden, Municipal Hospital Dresden, University Hospital Leipzig, University Hospital Halle). These data will be used to evaluate a trained neural network, which can classify liver fibrosis based on RF data.

To collect the necessary amounts of data, further centers are to be included in the course of the process. Thus, the study builds on previous analyses from *retrospective* data from the University Hospital Dresden (ethics application BO-EK-534122022) and is intended to test some of the promising preliminary results in a prospective approach.

### Design

The study is designed as a prospective, multicenter, experimental study. Female and male patients will be included who will receive a sonographic examination with reliable ground truth (depending on the local standard procedures of the center e.g. biopsy, contrast-enhanced ultrasound [CEUS], elastography, CT, MRI). In order not to create any additional effort, only patients with planned further clinical examinations are included. The data will then be used for validation by the already trained neural networks.

The prerequisites for participation are existing consent, the age of majority and no minor interventions on the liver within the last 14 days or within the last 14 days. Exclusion from major intervention within the last 6 months (see also 4. Test).

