## Initial more specific hypotheses:

1. The evaluation of RF data of the liver by neural networks with liver elastography results as a reference standard enables the detection and classification of degrees of steatosis, fibrosis and cirrhosis.
2. Neural networks trained on RF data are better than networks trained on B-scans at detecting degrees of steatosis, fibrosis, and cirrhosis as measured in AUC.
3. The diagnostic certainty of the degree of steatosis, fibrosis and cirrhosis of a neural network trained on RF data depends on the bandwidth of the US signal provided
4. The evaluation of RF data of the liver by neural networks with histology results as a reference standard enables the detection and classification of hepatic cavities.
5. The evaluation of RF data of the liver by neural networks with results of contrast ultrasonography as a reference standard enables the detection and classification of hepatic cavities.
6. Neural networks trained on RF data are better than networks trained on B-scans in classifying liver cavities.

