## 3. Study design

The study is designed as a prospective, multicenter, experimental study. Female and male patients undergoing sonographic examination with biopsy, CEUS or elastography will be included. It is important to ensure that the corresponding examinations would also be carried out independently of the study so as not to create any additional effort for the patient. The only difference is the additional systemic acquisition of raw ultrasound data, which is not always stored in conventional examinations.

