## Sample size planning

For the validation of the networks, a sample size of at least 200 patients is targeted. After completion of the data collection, each degree of fibrosis should be present about 20 times in order to enable a valid performance of the network for each degree of fibrosis. If this is not achieved, data collection will continue for 100 additional patients and then the distribution will be reviewed again. This is repeated until the target minimum number is reached. For focal

lesions we plan to include 50 patients per lesion. If this criterion is not met, data acquisition continuous.

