#### 4. Test Method

##### Study population

Female and male subjects over 18 years of age who are undergoing biopsy, CEUS, or elastography as part of an ultrasound scan.

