##### Inclusion Criteria

- Age over 18 years
- Subject's capacity to give consent
- Signed declaration of consent by the subject

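### The protocol contradicts itself on whether CT or MRI is an accepted reference, and its count of 50 patients per lesion, which decides when acquisition ends, has no reference condition

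*Protocol*

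**What the plan says.** **Accepted references.**
- The Design part of section 1 (Summary) includes patients with a reliable ground truth "depending on the local standard procedures of the center e.g. biopsy, contrast-enhanced ultrasound [CEUS], elastography, CT, MRI". The list is introduced as examples, so it is open, and it leaves the choice to each centre.
- Section 3 (Study design) is narrower: "Female and male patients undergoing sonographic examination with biopsy, CEUS or elastography will be included".
- The Study population paragraph of section 4 agrees with section 3. It takes adults "who are undergoing biopsy, CEUS, or elastography as part of an ultrasound scan".
- The inclusion criteria cover age, capacity and consent (the last item is "Signed declaration of consent by the subject") and name no reference examination.

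**Hypotheses (section 2).** Hypothesis 1, on diffuse disease, is set "with liver elastography results as a reference standard". Hypothesis 4 is set "with histology results as a reference standard enables the detection and classification of hepatic cavities". Hypothesis 5 makes the same claim against contrast ultrasonography. Hypotheses 2, 3 and 6 state no reference. CT and MRI appear in none of the six.

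**Focal-lesion target (section 3, Sample size planning).** The plan is 50 patients per lesion, with no condition on the reference. On a shortfall it says: "If this criterion is not met, data acquisition continuous".

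**Data linked to the images (section 4, Course of study).** The items are age, gender and the diagnosis taken from the doctor's letter. The set is then anonymized. The type of reference behind the diagnosis is not among the items.

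**The concern.** Two faults meet here.

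The first concerns eligibility. A centre that characterises liver lesions by MRI may enrol those patients under the Summary and may not under the Study population paragraph. The Goal section foresees further centres, and each could read the rule differently.

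The second concerns when recruitment stops. The 50 per lesion decides when focal-lesion acquisition ends, so what counts toward it matters. If the Summary governs, lesions referenced only by CT or MRI fill the count without meeting the reference stated in hypothesis 4 or 5. Acquisition could then end with fewer usable lesions for those two hypotheses than the target suggests. Because reference type is not a listed data item and the set is anonymized, it might not be possible to separate these lesions afterwards.

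**Working it through.** **Step 1: compare the texts.**

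| Place in protocol | Biopsy | CEUS | Elastography | CT / MRI | List |
|---|---|---|---|---|---|
| Section 1, Design | yes | yes | yes | yes | open |
| Section 3, Study design | yes | yes | yes | no | closed |
| Section 4, Study population | yes | yes | yes | no | closed |
| Section 4, Inclusion criteria | – | – | – | – | no reference named |

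The Study population paragraph also requires the examination to be part of an ultrasound scan, which CT and MRI are not. The inclusion criteria do not break the tie.

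**Step 2: match references to the lesion hypotheses.** This takes the focal lesions of the sample size section and the hepatic cavities of the hypotheses to be the same lesions, which is the natural reading.

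| Reference of the lesion | Hypothesis 4 | Hypothesis 5 | Hypothesis 6 | Counts toward 50 |
|---|---|---|---|---|
| Histology | yes | – | not excluded | yes |
| CEUS | – | yes | not excluded | yes |
| CT or MRI only, if the Summary governs | no | no | not excluded | yes |

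The third row is the problem: the lesion counts, but meets the stated reference of neither hypothesis 4 nor hypothesis 5.

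**Step 3: size.** The 50 has no stated power, effect size or precision behind it, so there is no figure in the plan to reproduce. What follows is illustration only. Let f be the share of a lesion type with CT or MRI as its only reference. The protocol gives no value, so f is assumed.

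- Lesions left for hypotheses 4 and 5 together: n = 50 × (1 − f).
- Patients needed to keep 50 such lesions: 50 / (1 − f), rounded up.
- 95% half-width for an assumed accuracy p: 1.96 × √(p(1 − p)/n).

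| f (assumed) | n | Needed to keep 50 | Half-width, p = 0.80 | Half-width, p = 0.90 |
|---|---|---|---|---|
| 0 | 50 | 50 | 0.111 | 0.083 |
| 0.10 | 45 | 56 | 0.117 | 0.088 |
| 0.20 | 40 | 63 | 0.124 | 0.093 |
| 0.30 | 35 | 72 | 0.133 | 0.099 |
| 0.50 | 25 | 100 | 0.157 | 0.118 |

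For example, at f = 0.20, n = 50 × 0.80 = 40 and 50 / 0.80 = 62.5, so 63 patients. At p = 0.80 the half-width is 1.96 × √(0.16/40) = 0.124. At f = 0.50, n = 25 and the half-width is 1.96 × √(0.16/25) = 0.157. These n are for hypotheses 4 and 5 combined; each alone may have fewer.

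**The case against.** The strongest defence is that sections 3 and 4 are the operative text. If they govern, a patient whose only further examination is CT or MRI is outside the study population, and lesions that fit neither hypothesis 4 nor 5 do not arise by this route. That is fair as far as it goes: the effect on the count depends on the Summary being followed. But nothing in the protocol says which text prevails, and the Summary is itself worded as an inclusion statement.

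Other parts of the defence also stand:

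- CT/MRI lesions are not useless to the study. Hypothesis 6 names no reference and could take them, and the study also aims to build a database.
- The 50 carries no claim of power or precision, so no stated inferential guarantee is broken. The Goal section states the evaluation use as fibrosis classification, so the stakes here are secondary.

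Three stronger readings are tempting, and the protocol does not support them:

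- A reader might infer that hypothesis 4 needs 50 histology cases for each lesion type, and so a very large enrolment where biopsy is rare. The protocol sets no separate count for hypothesis 4. A lesion with CEUS but no histology still serves hypothesis 5.
- A reader might infer that differences in accuracy between hypotheses 4 and 5 would be confounded by which lesions are biopsied. No comparison between the two is planned.
- A reader might infer that hypotheses 4 and 5 should be merged. That is a preference. Keeping them apart already separates results by reference.

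**Conclusion.** The point holds in this form: the protocol contradicts itself on whether CT or MRI suffices as ground truth for entry, and the rule that ends focal-lesion acquisition does not say which references count. Neither fault depends on an assumed number.

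The size of the consequence is unknown. It is conditional on the Summary's list being followed and on f, for which the protocol offers nothing. At f = 0.20 or 0.50, 40 or 25 of 50 lesions would be left for hypotheses 4 and 5 together, and the 95% half-width at an accuracy of 0.80 would widen from 0.111 to 0.124 or 0.157. If no lesion is referenced by CT or MRI alone, nothing is lost. In that case the contradictory wording and the unconditioned count remain, but without effect on these hypotheses through CT/MRI.

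That hypothesis 4 can speak only for biopsied lesions follows from using histology when section 3 allows only examinations that would be done anyway. This is a limit of scope to be stated, not an error.

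**What to change.** 1. Make the Design part of section 1, section 3 and the Study population paragraph of section 4 give one and the same list of accepted references.
2. In Sample size planning, count toward the 50 only lesions with a reference that hypothesis 4 or 5 accepts. If CT and MRI are kept, name them in a hypothesis.
3. Keep hypotheses 4 and 5 separate, and describe hypothesis 4 as applying to biopsied lesions.
4. In Course of study, add reference type to the items linked to the images before anonymization, so that lesions can be sorted by reference later.

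The cost is protocol wording, one extra data field at every centre and possibly a slower count toward the 50. No examinations are added. The data field is best settled before more data are collected: names are not kept with the study ID, so reference type could not readily be recovered afterwards.

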## 2. Objective of the study

# Study protocol for the acquisition and frequency spectroscopic evaluation of broadband clinical

ultrasound raw data for tissue and pathology differentiation using neural networks

Department of Medicine I, University Hospital Carl Gustav Carus at TU Dresden

The aim of the study is to collect liver-specific ultrasound raw data and images, collect them in the form of a multicenter, anonymized, local database and subsequently evaluate them spectroscopically using methods like convolutional neural networks (CNN). The networks were trained on retrospective data from a separate ethics application (BO-EK-534122022) and are to be validated in these data primarily, but not exclusively. Should a sufficient amount of data arise to enable sufficient training, the use of the data for the training of the Networks would also be a goal.

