##### Exclusion criteria

- minor intervention (e.g. biopsy) performed less than a week ago in the same area
- CEUS carried out less than a day ago
- Major intervention on the liver (e.g. resection) in the history

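### Training-set patients from University Hospital Dresden are not barred from the validation sample, and after anonymisation their records could no longer be identified and removed

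*Protocol*

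**What the plan says.** **Training source.** Section 2 of the protocol says: "The networks were trained on retrospective data from a separate ethics application (BO-EK-534122022". Section 1 (Goal) describes the earlier retrospective work as "data from the University Hospital Dresden (ethics application BO-EK-534122022".

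**Validation centres.** Section 1 (Goal) lists the prospective centres as "previously planned: University Hospital Dresden, Municipal Hospital Dresden, University Hospital Leipzig, University Hospital Halle", and further centres may join. Section 1 (Design) gives the purpose: "The data will then be used for validation by the already trained neural networks".

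**Eligibility.** Section 4 has three inclusion items: age, capacity to consent and "Signed declaration of consent by the subject". It has three exclusion items: a recent minor intervention in the same area, a recent CEUS, and "Major intervention on the liver (e.g. resection) in the history". The summary in section 1 (Design) words the intervention windows differently, but it too says nothing about membership of the training set.

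**Anonymisation.** Under section 4 (Course of study), age, gender and diagnosis are attached to the images. The combined set is then anonymised and stored for evaluation under a number that does not lead back to the person. Other centres anonymise locally before their data are merged in Dresden. Section 6 adds that the name is not kept with the study ID or the data, and that names survive only on paper information sheets.

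**Size.** Section 3 (Sample size planning) targets at least 200 patients and asks that "each degree of fibrosis should be present about 20 times". If this is not met, "data collection will continue for 100 additional patients", and the step is repeated as needed.

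**The concern.** The study is meant to test promising retrospective results prospectively, so the validation patients should be independent of the training patients. A liver patient of University Hospital Dresden whose earlier data trained the network may return for a planned elastography, meet every criterion and enter the validation set. The new recording is not the same file, but it comes from the same liver. A network may classify it better than a recording from a person it has never met. That would be patient-level leakage, and it would tend to make absolute accuracy look too good.

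Timing is what makes this a protocol matter. Leaving such patients out of an analysis can be specified later, but only if the records can still be recognised. The protocol removes that possibility before evaluation begins, and it describes no check, flag or centre code that would preserve it.

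**Working it through.** **Step 1: can overlap occur under the text?**

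| Question | Protocol text | Answer |
|---|---|---|
| Where do the training data come from? | Sections 1 (Goal) and 2 | University Hospital Dresden |
| Does that hospital recruit for validation? | Section 1 (Goal) | Yes, first-named centre |
| Does any criterion bar training patients? | Section 1 (Design); section 4, inclusion and exclusion | No |
| Is a check against the training set described? | Section 4 (Course of study); section 6 | No |
| Can a record be traced after anonymisation? | Section 4 (Course of study); section 6 | No; the paper sheets show who took part, not which record is theirs |

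Overlap is therefore permitted, and it cannot be undone once the data are anonymised.

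**Step 2: how large could the effect be?** The protocol gives no overlap share and no expected AUC, so there is no stated figure to reproduce. Every accuracy and overlap input below is an assumption.

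- A, AUC in new patients: 0.70 or 0.80.
- S, AUC in a new scan of a training patient: 0.85 or 0.90.
- f, share of validation patients who are in the training set: 5% or 10%.

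The model is a binormal mixture in which both groups are centred on a common cut-off:

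AUC(mix) = (1−f)²·A + f²·S + 2f(1−f)·C, with C = Φ((Φ⁻¹(A) + Φ⁻¹(S))/2).

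Example with A = 0.80, S = 0.90, f = 0.10: C = Φ((0.8416 + 1.2816)/2) = 0.8558. AUC(mix) = 0.81 × 0.80 + 0.01 × 0.90 + 0.18 × 0.8558 = 0.8110, a shift of 0.0110.

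| A | S | Shift at f = 5% | Shift at f = 10% |
|---|---|---|---|
| 0.80 | 0.85 | 0.0026 | 0.0052 |
| 0.80 | 0.90 | 0.0055 | 0.0110 |
| 0.70 | 0.85 | 0.0082 | 0.0163 |
| 0.70 | 0.90 | 0.0116 | 0.0230 |

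**Step 3: compare with sampling error.** The 95% half-width is 1.96 times the Hanley–McNeil standard error.

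| Split (diseased/not) | A = 0.80 | A = 0.70 |
|---|---|---|
| 100/100 (n = 200) | 0.062 | 0.072 |
| 20/180 (n = 200) | 0.120 | 0.133 |
| 200/200 (n = 400) | 0.043 | 0.051 |

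The shift is below the half-width in every case.

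**Step 4: what happens as n grows?** If the overlap share stays at 10%, the shift stays at 0.005–0.023 while the half-width narrows. If 20 overlapping patients are among the first 200 and none are added, the share at n = 400 is 20/400 = 5%, and the shift falls to 0.003–0.012.

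**Step 5: is 10% plausible?** If University Hospital Dresden supplied 25–50% of patients (assumed), 10% overall would mean 0.10/0.50 = 20% to 0.10/0.25 = 40% of its own participants. The protocol neither supports nor rules this out.

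**The case against.** **The effect is small and hypothetical.** Overlap is not shown, and the illustrated shift lies within sampling error. Both statements are true. They limit the weight of the point, but they do not answer it: the sponsor would have no means of learning afterwards whether overlap had occurred.

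**The bias need not persist.** A reader might infer that a fixed bias remains while blocks of 100 patients are added, so that confidence intervals eventually exclude the true value. That requires a constant overlap share. The networks are already trained, so the pool of training patients is finite, and section 1 (Goal) expects more centres. Both point towards dilution. Severe loss of interval coverage would need extreme inputs that nothing in the protocol supports.

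**AUC is named only in hypothesis 2.** That hypothesis compares RF with B-scan networks. Both networks could be affected by overlap there, and likewise in hypothesis 6, so a reader should not infer that the comparison favours RF. The point concerns absolute accuracy, as in hypothesis 1; AUC serves only as a convenient scale.

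**A check is still possible.** Staff meet each patient, and records are identifiable until anonymisation. This stands: nothing prevents a check before that step. What the protocol lacks is the instruction to make it.

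**Analysis sets belong in the SAP.** This stands in part. A SAP can define who is analysed, but it cannot restore an identity link that the protocol removes.

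**Repeat enrolment.** A reader might extend the point to patients enrolled twice in this study. Section 3 sets its totals in patients, and the effect would be slight: with 18 rather than 20 distinct patients in a degree, the Wilson half-width for a sensitivity of 0.80 goes from 0.168 to 0.176. That extension is not pursued.

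**Conclusion.** The point holds in a limited form and should be fixed. As written, the protocol admits training-set patients to the validation sample at University Hospital Dresden and then removes the means to identify them. The documents show that overlap is possible; they do not show that it occurs or how much there would be.

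Under the assumed inputs, any optimism in absolute AUC is modest: at most about 0.012 at 5% overlap and 0.023 at 10%, against a half-width of at least 0.062 at n = 200. The documents do not support a claim that the validation is invalid, or that the RF versus B-scan comparison is biased in a known direction. The case for acting rests on irreversibility and low cost rather than on a demonstrated large bias.

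**What to change.** In section 4 (Exclusion criteria and Course of study), add a step at University Hospital Dresden before anonymisation: check whether the patient is in the BO-EK-534122022 data set. Then do one of the following:

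- exclude that patient from the validation set; or
- store a training-set flag, so that the record stays in the database but is left out of the validation analysis.

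The protocol does not say whether the training list can still be searched by identity. If it cannot, keep a centre code with each record when the data are merged, and report the centres other than University Hospital Dresden separately as the independent validation.

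The cost is one or two sentences and one check or extra field. The downside is that a few flagged patients would not count towards the section 3 targets. With the flag, no record is lost to the database.

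### Does allowing later training on the prospective data undermine the validation of the networks?

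*Protocol*

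**What the plan says.** Three places in the protocol treat the prospective data as a test set. Section 1, Goal: "These data will be used to evaluate a trained neural network". Section 1, Design: "The data will then be used for validation by the already trained neural networks". Section 3, Sample size planning: "For the validation of the networks, a sample size of at least 200 patients is targeted".

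Section 2 gives the source of the networks, retrospective data under a separate ethics application, and says that they "are to be validated in these data primarily, but not exclusively". It then adds a second aim: "the use of the data for the training of the Networks would also be a goal". That aim is conditional, and the condition reads: "Should a sufficient amount of data arise to enable sufficient training".

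The sample size section sets two further counts. For fibrosis: "After completion of the data collection, each degree of fibrosis should be present about 20 times". The stated purpose is that the network's performance can be judged at each degree, and recruitment is extended in steps of 100 until the minimum is met. For focal findings: "lesions we plan to include 50 patients per lesion".

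**The concern.** The condition for training is circular, since it asks for enough data to train enough. The protocol does not say that validation must be finished first or that training must use other patients. The count per fibrosis degree is checked on the completed collection and the lesion count is a number to include, so neither is expressly limited to patients kept out of training.

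Two harms are conceivable. If a network is trained on prospective patients and then tested on them, its AUC, the measure named in hypothesis 2, will tend to be too favourable. If patients are split instead, a scarce degree or lesion type could have fewer test patients than the plan calls for, while the recruitment check is still formally met. A patient once used for training cannot serve again as an unseen patient for that network, so the order of the two uses matters.

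**Working it through.** **Plan's own figures.** The targets of 200, about 20 and 50 come with no alpha, power, effect size or precision. They are count targets, so there is nothing to reproduce.

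**Case A: validation as written.** The networks are already trained on other patients. The training share taken from the prospective set is t = 0, and all 200, about 20 per degree and 50 per lesion are unseen test patients. Training a further network on these patients afterwards does not alter that result.

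**Case B: a share t is removed for training before testing.** The protocol gives no t; 0.2 to 0.8 is assumed. Test patients left = n(1 - t). Collection needed to keep n for testing = n/(1 - t), rounded up.

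| t | Left of 20 per degree | Left of 50 per lesion | Left of 200 | Needed to keep 20 / 50 / 200 |
|---|---|---|---|---|
| 0.2 | 16 | 40 | 160 | 25 / 63 / 250 |
| 0.5 | 10 | 25 | 100 | 40 / 100 / 400 |
| 0.8 | 4 | 10 | 40 | 100 / 250 / 1000 |

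**Precision for sensitivity.** Exact (Clopper-Pearson) 95% intervals, assuming 80% observed:

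- Degree: 16/20 gives 0.563 to 0.943; 8/10 gives 0.444 to 0.975.
- Lesion type: 40/50 gives 0.663 to 0.900; 20/25 gives 0.593 to 0.932.

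**Precision for AUC, one degree against the rest.** Hanley-McNeil variance = [A(1 - A) + (m - 1)(A/(2 - A) - A²) + (k - 1)(2A²/(1 + A) - A²)]/(mk), with m patients in the degree and k others.

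- A = 0.80, m = 20, k = 180: (0.16 + 19 × 0.0267 + 179 × 0.0711)/3600 = 0.00372; SE 0.061; half-width 1.96 × SE = 0.120.
- A = 0.80, m = 10, k = 90: (0.16 + 9 × 0.0267 + 89 × 0.0711)/900 = 0.00748; SE 0.086; half-width 0.169.
- A = 0.70, same two settings: 0.133 and 0.189.

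**Which case does the protocol describe?** The Goal and Design paragraphs send the data to networks already trained, and Section 2 says where that training took place and ranks validation first. The sample size section ties the 200 to validation and the 20 per degree to judging performance. Under these statements the collection and the test set are the same patients, which is Case A. Case B needs a step that no section plans.

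The loss shown in Case B is also a worst case. It takes a degree at exactly 20 and removes half, although Section 2 allows training only once enough data have arisen. A degree with 40 patients still keeps 20 at t = 0.5. With patient-level cross-validation, each patient would be tested once by a model that had not seen that patient, and the test counts would not fall at all.

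**The case for a change.** The strongest argument for a change is that the role of the only prospective dataset is a design decision, not an analysis detail. The protocol grants an open permission in its objectives beside validation-only wording elsewhere, and a few sentences would close the gap with no extra patients for the validation itself.

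Part of this stands. Section 2 does leave the threshold, the order and the separation of patients unstated, and the degree and lesion counts do not expressly reserve anyone from training. But the two kinds of wording do not contradict each other: Section 2 itself says that validation is the primary use and not the only one, and then names the second use. Patient-level splits, locking of models and the order of validation and retraining are matters that a protocol commonly leaves to the statistical analysis plan.

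The claim that the counts do not describe test patients goes too far, because the 200 are named for validation and the 20 per degree carry a validation purpose. A fuller rule that assigned separate cohorts to each group of hypotheses would add an allocation that the protocol does not make.

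**Conclusion.** No change is needed. The planned validation is independent as written and loses no patients. Harm would arise only if prospective patients were used for training before or alongside that validation, either without separating them from the test patients or with a split that cut the test set. No section plans this.

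Under an assumed 50% training share, the cost for a degree at exactly 20 would be 10 test patients instead of 20, and an AUC half-width of about 0.17 instead of 0.12 at an assumed AUC of 0.80. With validation done first, or with training confined to surplus patients, that cost is zero. The open point concerns a secondary, conditional aim. Ordinary practice settles it: validate the fixed networks first, and report a retrained network only on patients it was not trained on. The conclusion rests on reading the networks to be validated as those trained on the retrospective data, which Section 2 states.
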